3.3.2. Exclusion Criteria

Subjects meeting any of the following criteria will be excluded from enrollment:

1. HER-2 overexpressed/amplified MBC (Appendix 2 for guidelines from ASCO);
2. ER and or PR expressing tumors;

3. Is currently participating and receiving study therapy or has participated in a study of an investigational agent and received study therapy or used an investigational device within 28 days prior to enrollment;
4. Patients who have a history of allergic reactions attributed to compounds of similar chemical or biologic composition to leronlimab (PRO 140) are not eligible;
5. Patients who have had prior exposure to CCR5 antagonists are not eligible;
6. Patients who have a known additional malignancy that is progressing or requires active treatment are not eligible. Patients who have had a prior diagnosis of cancer and if it has been <3 years since their last treatment are not eligible. Exceptions include basal cell carcinoma of the skin or squamous cell carcinoma of the skin that has undergone potentially curative therapy or in situ cervical cancer;
7. Has an active infection requiring systemic therapy. Note: Patients must complete any treatment with antibiotics prior to registration;
8. Patients who have a known HIV positive status or known/ active Hepatitis B and/or C infection are not eligible;
9. Has known active central nervous system (CNS) metastases and/or carcinomatous meningitis. Note: Subjects with previously treated brain metastases may participate provided they are stable (without evidence of progression by imaging for at least four weeks prior to the first dose of trial treatment and any neurologic symptoms have returned to baseline), have no evidence of new or enlarging brain metastases, and are not using steroids for at least 7 days prior to trial treatment. This exception does not include carcinomatous meningitis which is excluded regardless of clinical stability;
10. Has a history or current evidence of any condition, therapy, or laboratory abnormality that might confound the results of the trial, interfere with the subject's participation for the full duration of the trial, or is not in the best interest of the subject to participate, in the opinion of the treating investigator;
11. Has known psychiatric or substance abuse disorders that would interfere with cooperation with the requirements of the trial; and
12. Is pregnant or breastfeeding, or expecting to conceive or have children within the projected duration of the trial, starting with the pre-screening or screening visit through the duration of study participation.

4 STUDY SCHEDULE

The total study duration for each subject consists of pre-screening, screening, treatment, and follow-up periods. A study flow diagram is presented in [Figure 4-1](#).

- (1) Pre-Screening Period:** A separate Informed Consent Form (ICF) will be used for the pre-screening. The pre-screening period is designed for evaluation of histologically confirmed diagnosis of mTNBC (documented by HER-2 negative, ER<1%, PR<1%) and CCR5 positive expression by Immunohistochemistry (IHC) assay. This assay will be performed in archival tissue from previous biopsy specimens. If archival tissue is not available then, fresh core or excisional biopsy will be done. If patient qualifies, then they will undergo full screening.
- (2) Screening Period:** Screening assessments will commence after obtaining signed informed consent, and will include review of medical and medication history, demographic information and baseline disease characteristics, eligibility evaluation, physical examination, vital signs, height and weight, concomitant medications, electrocardiogram (ECG), tumor imaging assessment, routine serum biochemical, hematologic, urinalysis, serum pregnancy (if applicable). These assessments must be conducted within 28 days of the first treatment visit.
- (3) Treatment Period:** Subjects who meet the eligibility criteria will have completed following evaluations and assessments before receiving treatment: a) review of medical and medication history; b) physical examination, vital signs and documentation of ECOG performance status; c) ECG; d) routine serum biochemical, hematologic, urine pregnancy (if applicable) and urine laboratory assessments. Additionally, a blood sample will be collected prior to treatment administration for CTCs PD-L1/CCR5 and CTC - CAMLs analysis.

Each treatment cycle will consist of 21 days. Leronlimab (PRO 140) will be administered subcutaneously weekly on Days 1, 8, and 15 in combination with carboplatin AUC 5 on Day 1 of each cycle (every 21 days). Day 1 of Cycle 2 begins at Day 22. The study treatment will be administered by a licensed medical professional at clinic site or self-administered by subjects at home.

Note: All leronlimab (PRO 140) SC weekly injections at Cycle 1 (Days 1, 8, and 15) and at Day 1 of subsequent cycles must be administered at clinic. The remaining study treatment injections at Day 8 and Day 15 (beyond Cycle 1) may be self-administered by subjects at home after proper training by a healthcare professional.

Subjects will be allowed to continue treatment under subsequent treatment cycles until any one of the following occurs: progressive disease or unacceptable toxicity or withdrawal of consent.

(4) Follow-Up Period: An End of Treatment (EOT) visit will be conducted 30 (\pm 3) days after the last treatment visit (i.e., after last dose of leronlimab (PRO 140) and carboplatin). Additionally, follow-up will be done for survival status, by clinic visits or phone or another method of contact, every 3 months (\pm 1 month) for 2 years after treatment discontinuation or until death, whichever occurs first.

Figure 4-1: Study Flow Diagram

[figure not shown]

Table 4-1: Schedule of Assessments

Tests and Assessments		Screening Period						Treatment Period						Follow-up Period	
Visit	Day(s)	Treatment Cycle 1 (21 days)			Treatment Cycle 2 (21 days)			Additional Treatment Cycles			EOT	Survival Follow-ups			
		Pre-Screening Visit [1]	Screening Visit	C1D1	C1D8	C1D15	C2D1	C2D8	C2D15	CXD1	CXD8	CXD15			
Window		Within 28 Days from Screening visit	Day 1	Day 8	Day 15	Day 22	Day 29	Day 36							
Informed Consent [2]		X	X												
Demographics and Baseline Disease Char.		X													
Medical and Medication History [3]		X	X												
Vital Signs [4]		X	X	X	X	X	X	X	X	X	X	X	X	X	X
Height and Weight		X	X[5]												
Physical Exam		X	X	X[6]	X	X[6]	X	X[6]	X	X[6]	X	X[6]	X	X	X
ECOG Performance Status		X	X												
Electrocardiogram, 12-lead [7]		X	X												
Toxicity assessment (post treatment)			X												
Tumor Imaging Assessment [8]			X												
Complete Blood Count [9]		X	X[25]												
Biochemistry [10]		X	X[25]												
Urinalysis [11]		X	X[25]												
Serum Pregnancy test [12]		X													
Urine Pregnancy test [12]			X												
Eligibility Assessment		X	X	X											
Enrollment / Cohort Assignment		X													
Blood sample collection for CTCs PD-L1 /CCRS Analysis [13]			X												
Blood sample collection for CTC and CAMLs Analysis [14]			X												
Tissue for CCR5 (archival or fresh biopsy)			X[15]												
Tissue for PD-L1 expression level			X[16]												

Tests and Assessments		Screening Period		Treatment Cycle 1 (21 days)				Treatment Cycle 2 (21 days)				Additional Treatment Cycles				Follow-up Period	
Visit	Day(s)	Pre-Screening Visit [1]	Screening Visit [1]	C1D1	C1D8	C1D15	C2D1	C2D8	C2D15	C3D1	C3D8	C3D15	C4D8	C4D15	EOT	Survival Follow-ups	
				Day 1	Day 8	Day 15	Day 22	Day 29	Day 36								
Window				Within 28 Days from Screening visit	7 (± 1) Days from C1D1 visit	7 (± 1) Days from C1D8 visit	7 (± 1) Days from C1D15 visit	7 (± 1) Days from C2D1 visit	7 (± 1) Days from C2D8 visit	7 (± 1) Days from C3D1 visit	7 (± 1) Days from C3D8 visit	7 (± 1) Days from C3D15 visit	7 (± 1) Days from C4D8 visit				
lerolimab (PRO 140) administration [17]				X	X	X	X	X	X	X	X	X	X	X	X		
Carboplatin administration [18]				X			X				X						
Post Injection Site Evaluation by Investigator [19]				X	X	X	X	X	X	X	X	X	X	X	X		
Injection Site Pain Assessment (VAS) [20]					X	X	X	X	X	X	X	X	X	X	X	X[20]	
Survival status																X	
Concomitant medications				X	X	X	X	X	X	X	X	X	X	X	X	X[23]	
Adverse Events				X	X	X	X	X	X	X	X	X	X	X	X		

Footnotes

- [1] A separate Informed Consent Form (ICF) will be used for the pre-screening. The pre-screening period is designed for evaluation of histologically confirmed diagnosis of mTNBC (documented by HER-2 negative, ER<1%, PR<1%) and CCR5 positive expression by Immunohistochemistry (IHC) assay. This assay will be performed in archival tissue from previous biopsy specimens. If archival tissue is not available then, fresh core or excisional biopsy will be done. If patient qualifies, then they will undergo full screening.
- [2] Informed consent must be obtained prior to patient participation in any protocol-related activities that are not part of routine care.
- [3] A complete review of the subject's past medical history (including all prior anti-tumoral therapy related to breast cancer), past surgeries, and current therapies (medications and non-medications) will be undertaken by the Investigator to check that all inclusion and no exclusion criteria have been met.
- [4] Vital signs include blood pressure, heart rate, respiration rate, and temperature will be measured at clinic visit.
- [5] Weight only
- [6] Symptom-directed physical examination at clinic visits
- [7] A 12-lead ECG will be repeated during the study only if clinically indicated and at the discretion of the treating physician.

[8] Scans are to be done at the end of 2 cycles (i.e., every 6 weeks; [1-3 days before next cycle begins]) for the first 6 cycles (18 weeks) and at end of 3 cycles (i.e., every 9 weeks; [1-3 days before next cycle begins]) thereafter, and at End of Treatment (EOT) visit by CT, PET/CT or MRI with contrast (per treating investigator's discretion) using the same method as at baseline. Tumor measurements will be done using RECIST v1.1. To be assigned a status of PR or CR, changes in tumor measurements must be confirmed by repeat assessments that should be performed 6 weeks after the criteria for response are first met. In the case of SD, measurements must have met the SD criteria at least once after study entry at a minimum interval of 6 weeks.

[9] Hemoglobin, Hematocrit (HCT), Red Blood Cells (RBC), White Blood Cells (WBC) with total and differential count, absolute lymphocyte count, absolute neutrophil count (ANC) and platelets.

[10] Serum Biochemistry will include:
Hepatic function indicators: total bilirubin, direct bilirubin, alkaline phosphatase, aspartate aminotransferase (AST)/SGOT, alanine aminotransferase (ALT)/SGPT, albumin and total protein.
Renal function indicators: blood urea nitrogen (BUN), creatinine
Electrolytes: sodium, potassium, chloride, calcium and bicarbonate
Other: glucose (random)

[11] Urine samples will be tested for pH, appearance, color, specific gravity, turbidity, ketones, bilirubin, blood, glucose, protein, nitrites, urobilinogen, and leukocyte esterases. Microscopic exam includes bacteria, cast, crystals, epithelial cells, RBC and WBC.

[12] Only performed on women of childbearing potential

[13] Blood sample collection for CTCs PD-L1/CCR5 analysis to be taken prior to the treatment administration at baseline (C1D1), on Day 1 (CXD1) of each subsequent cycle, and at the end of treatment (EOT).

[14] Blood sample collection for CTC and CAMLs analysis to be taken prior to treatment administration at baseline (C1D1), on Day 1 (CXD1) of each subsequent cycle, and at the end of treatment (EOT).

[15] Archival breast tissue (primary or metastatic site) will be collected from all patients at the pre-screening period and analyzed for presence of CCR5. Note: If no archival tissue is available, fresh biopsy to be done of the primary or metastatic site.

[16] Breast tissue (primary or metastatic site) collected to analyze for the presence of CCR5 will additionally be used for evaluating PD-L1 expression levels. The PD-L1 expression testing will be performed at the reference laboratory using the formalin-fixed, paraffin-embedded (FFPE) tissue block or slides.

[17] Leronlimab (PRO 140) is administered as subcutaneous injection in the abdomen weekly. A total of 350mg or 525 mg or 700mg (175 mg/mL) is delivered as two injections on opposite sides of the abdomen. The 350mg dose will be delivered as two injections of 1 mL each, 525mg dose will be delivered as two injections of 1.5 mL each and 700mg dose will be delivered as two injections of 2 mL each.

[18] Carboplatin will be IV infused at AUC 5 on D1 of each cycle, every 3 weeks

- [19] Injection Site Reaction Assessment as assessed by Investigator (or designee) at the clinic visits. Injection Site Reaction Assessment will not be applicable if leronlimab (PRO 140) is self-administered by subjects at home.
- [20] Subject-perceived injection site pain (average pain since last treatment) will be assessed using the Pain Visual Analog Scale (VAS) prior to each study treatment administration which evaluates average pain since last treatment. Injection Site Pain Assessment will not be applicable if leronlimab (PRO 140) is self-administered by subjects at home.
- [21] Subjects will be followed up by clinic visits or phone call or another method of contact, for survival status every 3 months (± 1 month) for 2 years after treatment discontinuation or until death, whichever occurs first
- [22] All subjects will be followed for adverse events for 30 days after last dose of leronlimab (PRO 140) and carboplatin, or until the subject starts a new treatment, whichever occurs first.
- [23] Subjects who discontinue treatment for unacceptable adverse event(s) will be followed until resolution or stabilization of the adverse event (i.e. the grade is not changing). If a subject stops treatment due to unacceptable adverse event(s) but has not demonstrated disease progression, then the subject will be followed with imaging studies every 9 weeks until the time of progression radiographically according to RECIST v1.1 criteria. In the event that a radiographic response is detected, then this event will be included as a response in the final analysis, and the time of progression used in calculation of the survival analysis.
- [24] Limited to all subsequent anti-cancer treatments.
- [25] Can be performed within 3 days prior to each cycle start.

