- d. The occurrence in any subject of a life-threatening SAE whose causal relationship to leronlimab (PRO 140) is judged to be probable or definite
- e. The occurrence of one or more non-life-threatening SAEs whose causal relationship to leronlimab (PRO 140) is judged to be definite
- f. The occurrence, in one or more subjects, of Grade 4 laboratory abnormalities, judged to be probably or definitely related to receipt of leronlimab (PRO 140)
- g. The occurrence of hematologic and non-hematological adverse events, judged to be possibly, probably or definitely related to receipt of leronlimab (PRO 140) based on previous clinical experience and that are of CTCAE Grade 3 or greater severity. Permissible exceptions to this rule include Grade 3 fatigue of less than one week duration, and Grade 3 nausea, vomiting, and diarrhea that resolve within 48 hours following institution of appropriate supportive care.
- h. Hy's law
- i. Neutropenic fever
- j. Grade 4+ neutropenia or thrombocytopenia >7 days
- k. Grade 3+ thrombocytopenia with bleeding
- l. Grade 3+ electrolyte abnormality that lasts >72 hours, unless the patient has clinical symptoms, in which case all grade 3+ electrolyte abnormality regardless of duration should count as a DLT. Grade 3+ amylase or lipase elevation NOT associated with symptoms or clinical manifestations of pancreatitis does not need to be counted as a DLT
- m. For patients with hepatic metastases, AST or ALT >8xULN or AST or ALT >5x ULN for ≥ 14 days

If any of the SAEs or DLTs outlined above have occurred, the Data Safety Monitoring Board (DSMB) will conduct an independent review of the data and make a final decision for dose escalation to the next cohort.

The dosing regimen for each cohort is as follows:

- Cohort A: 350 mg leronlimab (PRO 140) SC weekly + AUC 5 Carboplatin every 3 weeks
- Cohort B: 525 mg leronlimab (PRO 140) SC weekly + AUC 5 Carboplatin every 3 weeks
- Cohort C: 700 mg leronlimab (PRO 140) SC weekly + AUC 5 Carboplatin every 3 weeks

Leronlimab (PRO 140) is administered as subcutaneous injection in the abdomen weekly. A total of 350 mg, 525 mg, or 700 mg (175 mg/mL) is delivered as two injections on opposite sides of the abdomen. The 350 mg dose will be delivered as two injections of 1 mL each, 525 mg dose will be delivered as two injections of 1.5 mL each and 700 mg dose will be delivered as two injections of 2 mL each.

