6.2.10. Carboplatin - Side effects

1. Hematologic: Thrombocytopenia (dose limiting), neutropenia, leukopenia, anemia.
2. GI: Nausea and vomiting (frequent but less severe than with cisplatin), treatable with appropriate antiemetic prophylaxis.
3. Anorexia, diarrhea and constipation have also been reported.
4. Dermatologic: Rash, urticaria. Rarer reactions include alopecia, mucositis, and hypersensitivity reactions.
5. Hepatic: Abnormal liver function tests, usually reversible with standard doses.
6. Neurologic: Rarely peripheral neuropathy is seen. May be more common in patients greater than 65 years of age. May also be cumulative, especially in patients with prior cisplatin treatment.
7. Ototoxicity (rare).
8. Renal: Elevations in serum creatinine, BUN; electrolyte loss (Mg, K, Na, Ca).
9. Miscellaneous: Pain, asthenia, flu-like syndrome.

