7.11 CLINICAL LABORATORY ASSESSMENTS

Blood samples will be collected for analysis of the following parameters:

- Biochemistry and Complete Blood Count (CBC) Parameters: At Screening and Day 1 of each treatment cycle and at the end of treatment (EOT).
- Serum pregnancy test (for female subjects of childbearing potential): At Screening
- Urine pregnancy test (for female subjects of childbearing potential): At Day 1 of each treatment cycle
- CTCs PD-L1/CCR5 Analysis: At Day 1 of each treatment cycle and at the end of treatment (EOT).
- CTC and CAMLs Analysis: At Day 1 of each treatment cycle and at the end of treatment (EOT).

All laboratory reports will be reviewed by the Investigator. Abnormal results that are considered by the Investigator to be clinically significant, will be recorded as adverse events. If in the Investigator's judgment, in order to make the determination of clinical significance the testing may be needed to be repeated. Validated, quality-controlled laboratory data will be transferred to the main database for analyses.

Table 7-2: Central Lab Parameters

CBC Parameters	Biochemistry Parameters	Urinalysis
Hemoglobin	Liver Function Tests	pH
Hematocrit	Total Bilirubin	Appearance
RBC count	Direct Bilirubin	Color
WBC count	Alkaline Phosphatase (ALP)	Specific gravity
WBC Differential	Alanine Aminotransferase (ALT) (or SGPT)	Turbidity
Absolute lymphocyte count	Aspartate Aminotransferase (AST) (or SGOT)	Ketones
Absolute neutrophil count	Albumin	Bilirubin
Platelet count	Total Protein	Blood
Miscellaneous		Glucose
Serum pregnancy test	Renal Function Tests	Protein
Urine pregnancy test	blood urea nitrogen (BUN)	Nitrites
(for female subjects of childbearing potential)	Creatinine	Urobilinogen
Tissue for CCR5 expression (archival or fresh biopsy)	Electrolytes	Leukocyte esterases
Tissue for PD-L1 expression (archival or fresh biopsy)	Sodium	Microscopic exam includes bacteria, cast, crystals, epithelial cells, RBC and WBC.
CTCs PD-L1/CCR5	Potassium	
CTC CAMLs	Chloride	
	Calcium	
	Bicarbonate	
	Other:	
	Glucose, Random, Serum	

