8.5 INTERIM ANALYSIS

No interim analysis (IA) will be performed for efficacy. There will be a safety review, once all three (or six) subjects from each cohort complete the DLT evaluation period (defined as cycle 1 or the first 21 days of treatment).

The Sponsor's Medical Monitor, CRO Medical Monitor and study investigators must be satisfied with data obtained in Cohort A before allowing subsequent enrollment of Cohort B. Likewise, they must be satisfied with data obtained in Cohort B before allowing subsequent enrollment in Cohort C.

In addition, should any of the following events occur in any cohort during the DLT evaluation period, the Data Safety Monitoring Board (DSMB) will meet to review available study data and make a final decision for dose escalation to the next cohort:

- a. Death in any subject in which the cause of death is judged to be possibly, probably or definitely related to leronlimab (PRO 140)
- b. The occurrence in any subject of an anaphylactic reaction to leronlimab (PRO 140)
- c. The occurrence in any subject of a severe local injection site reaction (Grade 3 which is not resolved or recurs; or Grade 4) that precludes administration of consecutive leronlimab (PRO 140) doses.
- d. The occurrence in any subject of a life-threatening SAE whose causal relationship to leronlimab (PRO 140) is judged to be probable or definite
- e. The occurrence of one or more non-life-threatening SAEs whose causal relationship to leronlimab (PRO 140) is judged to be definite
- f. The occurrence, in one or more subjects, of Grade 4 laboratory abnormalities, judged to be probably or definitely related to receipt of leronlimab (PRO 140)
- g. The occurrence of hematologic and non-hematological adverse events, judged to be possibly, probably or definitely related to receipt of leronlimab (PRO 140) based on previous clinical experience and that are of CTCAE Grade 3 or greater severity. Permissible exceptions to this rule include Grade 3 fatigue of less than one week duration, and Grade 3 nausea, vomiting, and diarrhea that resolve within 48 hours following institution of appropriate supportive care.
- h. Hy's law
- i. Neutropenic fever
- j. Grade 4+ neutropenia or thrombocytopenia >7 days
- k. Grade 3+ thrombocytopenia with bleeding

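### No scheduled visit measures magnesium, although DLT item l counts any Grade 3+ electrolyte abnormality and the protocol lists magnesium loss as a carboplatin effect

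*Protocol*

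**What the plan says.** Item l of the DLT list in Protocol section 3 covers a "Grade 3+ electrolyte abnormality that lasts >72 hours, unless the patient has clinical symptoms". Where symptoms are present, an abnormality of that severity qualifies however long it persists. The same item appears in the synopsis, in Protocol sections 8.5 and 12, and in SAP section 4. It does not say which electrolytes it means. Unlike items d to g, it does not ask whether the event is related to leronlimab.

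Protocol section 6.2.10, under the renal effects of carboplatin, names "electrolyte loss (Mg, K, Na, Ca").

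The serum biochemistry list in Protocol Table 4-1 footnote 10 gives "Electrolytes: sodium, potassium, chloride, calcium and bicarbonate". Protocol section 7.11 ("Table 7-2: Central Lab Parameters") and SAP Appendix 1 footnote 10 list the same five analytes. Section 6.2.11, on nursing implications for carboplatin, asks for blood counts and attention to fluid status but does not mention magnesium.

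Protocol section 7.11 schedules biochemistry "At Screening and Day 1 of each treatment cycle and at the end of treatment (EOT"). Table 4-1 footnote 25 adds "Can be performed within 3 days prior to each cycle start". Protocol section 8.5 sets the "DLT evaluation period (defined as cycle 1 or the first 21 days of treatment").

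**The concern.** The MTD is the Phase Ib primary endpoint and is decided by DLT counts in three to six patients per level. Before escalation, the PI must determine that none of the listed events has occurred. For magnesium, that determination would rest on no scheduled data, even though the protocol names magnesium loss as an effect of the background drug and item l counts electrolyte events whichever drug caused them.

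A single event matters in a 3+3 design. It separates 0 of 3 (escalate) from 1 of 3 (expand), and 1 of 6 (escalate) from 2 of 6 (stop). An event that is never measured can only lower the observed count. The laboratory summaries and shift tables in SAP section 8.4.3 would also contain nothing on this listed carboplatin effect.

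**Working it through.** **1. Analytes.** The plan has no figure to reproduce here, so the first check compares lists.

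| Carboplatin losses listed in Protocol 6.2.10 | In the panel (Table 4-1 fn 10, Table 7-2, SAP App. 1 fn 10)? |
|---|---|
| Magnesium | No |
| Potassium | Yes |
| Sodium | Yes |
| Calcium | Yes |

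One of the four named losses is unmeasured. The three panel lists are intact and agree with each other, so this is not a text-extraction fault. The number of scheduled visits with a magnesium test is 0.

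**2. Scheduled chemistry in the DLT window.** Inputs: a window of Days 1 to 21 (Protocol 8.5); chemistry on Day 1 of each cycle (7.11); draws allowed up to 3 days before cycle start (Table 4-1 fn 25); visits 7 ± 1 days apart (Table 4-1). Protocol section 4 places the Cycle 1 Day 1 chemistry before treatment.

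- Nominal Cycle 2 Day 1 = 1 + 7 + 7 + 7 = Day 22. The draw can fall on Day 22 - 3 = 19 through Day 22.
- With all visit windows, Cycle 2 Day 1 runs from 1 + 6 + 6 + 6 = Day 19 to 1 + 8 + 8 + 8 = Day 25. The draw can therefore fall on Day 19 - 3 = 16 through Day 25.
- Scheduled post-dose draws within Days 1 to 21: 1 if that sample is taken by Day 21, otherwise 0.

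Showing that an abnormality lasted more than 72 hours takes at least two values more than 3 days apart. Scheduled draws supply at most one, and this holds for sodium, potassium and calcium as well as magnesium.

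**3. How often an event could arise.** The documents give no frequency or grade for magnesium loss. Taking the Cycle 1 rate p of a qualifying event as an assumption, the chance of at least one among n patients is 1 - (1 - p)^n.

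| Assumed p | n = 3 | n = 6 |
|---|---|---|
| 2% | 1 - 0.98^3 = 6% | 1 - 0.98^6 = 11% |
| 5% | 1 - 0.95^3 = 14% | 1 - 0.95^6 = 26% |
| 10% | 1 - 0.90^3 = 27% | 1 - 0.90^6 = 47% |

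These are chances that an event occurs. They equal the chance of an uncounted event only if no discretionary test picks it up, so they are upper limits on missed events at each assumed rate.

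**The case against.** The strongest reply is that the omission is narrow and its effect on the MTD is not shown. Taking its parts in turn:

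- **Detection is not impossible.** A reader might infer that a magnesium DLT cannot be found at any visit. The documents do not support that. Protocol section 4.5 leaves tests at unscheduled visits to the investigator, section 9.1 has adverse events elicited by direct questioning, and a symptomatic Grade 3+ abnormality counts at any duration, so symptoms could prompt a test. This stands. What remains is that no scheduled test would find it.
- **A wrong MTD is not demonstrated.** A reader might also infer that the MTD will be set too high. Carboplatin is held at AUC 5 in every cohort, no text suggests that magnesium loss rises with leronlimab dose, a listed side effect is not the same as an expected Grade 3+ event, and the DSMB reviews the data before the final MTD decision. This stands too. Only the direction of any bias follows from the documents.
- **Adding magnesium does not make the 72-hour rule work.** This is correct, as step 2 shows. It does not remove the analyte gap, since better-timed samples would still omit magnesium. A Grade 3+ value on the existing sample can also prompt a repeat, which section 7.11 allows, and a symptomatic one needs no duration.
- **Amylase and lipase.** Item l exempts asymptomatic elevations of these enzymes, and neither is in the panel. A reader might take this as a second gap. It is not: an exemption can govern values found incidentally and needs no scheduled assay. Removing it could change what counts as a DLT, which is a clinical rule outside this point.

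**Conclusion.** The point holds in a limited form. As written, the plan leaves one of the four electrolytes it names as depleted by carboplatin untested at every scheduled visit, while a primary-endpoint criterion covers electrolyte abnormalities without exception for that one. Magnesium DLTs would surface only through discretionary testing, and asymptomatic ones would probably go uncounted. Any bias in the DLT count is downward.

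The size of that bias cannot be derived from the documents. The range of 6% to 27% in three patients and 11% to 47% in six rests wholly on assumed rates of 2% to 10%, independence between patients and, if read as missed events, no unscheduled testing. The omission itself is certain; an effect on the selected dose is possible but not shown. The correction is worth making because it is cheap and improves both DLT ascertainment and routine safety monitoring.

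**What to change.** Add serum magnesium to the biochemistry list in Protocol Table 4-1 footnote 10, Protocol Table 7-2 and SAP Appendix 1 footnote 10, run on the biochemistry sample already drawn. It would then enter the laboratory summaries in SAP section 8.4.3 with the other analytes. The cost is one extra assay per existing sample and an edit to three lists; no extra visit or blood draw is needed for this step.

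Separately, reconcile item l with the Cycle 1 laboratory schedule. The duration criterion and the draw times do not fit together for any electrolyte, and the sponsor should state how a duration above 72 hours is to be established. How that is resolved is the sponsor's clinical decision; if it adds a Cycle 1 draw, that carries its own cost. The amylase and lipase wording needs no change on this account.
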